#### Primary endpoints:

- 10-year and lifetime breast cancer risk and the corresponding NICE risk categories for two risk prediction models: i) TCv8 and ii) BOADICEA v5.
- Risk scores from TCv8 and BOADICEA will be assessed using different model inputs: i) classical factors alone, ii) classical factors plus mammographic density (BIRADS) and iii) classical factors plus mammographic density plus SNPs.

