## 1.0 STUDY PROTOCOL

### 1.1 Research abstract

Estimation of breast cancer risk is important since it enables selection of a high and moderate risk population who benefit from more frequent breast screening and the introduction of targeted measures to reduce risk such as lifestyle change, chemoprevention and risk reducing surgery. Traditionally, risk is estimated by combining information concerning family history and non-familial factors, such as age of menarche and first pregnancy. Subsequent management is related to the degree of risk (high, moderate or average) according to NICE guidelines. Members of the research team and others have added mammographic density (MD) and breast cancer risk associated single nucleotide polymorphisms (SNPs) to risk models which improves the accuracy of risk estimation but which may change the original given risk and risk management given before the updated models became available. The objective of this study is to quantify change in risk and risk management when MD and SNPs are incorporated into two standard models (Tyrer-Cuzick v8 & BOADACEA V). A second objective of the study is to determine the psychological effects of change of risk and management. This study will use participant data from the Family History Risk (FH-Risk) study to recalculate risk. The FH-Risk study population consists of 954 women referred to the Family History Risk and Prevention Clinic (FHRPC) between 2000 and 2012 who gave informed consent for DNA testing and estimation of MD as part of the FH-Risk study which recruited between 2010 and 2012. Change in risk and management will be calculated by comparing given risk at the time of clinic entry compared with re-estimated risk when MD and SNPs are added to the risk models according to NICE guidelines. Risk will be estimated retrospectively at the time of entry to the clinic and the time of latest follow up. All of those who took part in the FH-Risk study will be given the opportunity to discuss their updated risk.

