**Models for assessment of breast cancer risk.**

Early observations on the greater incidence of breast cancer in nuns and the increased effect on risk of older age of first birth (Ramazzini 1713, MacMahon 1970) and family history (Broca 1866, Lynch & Krush 1966) suggested that both reproductive/lifestyle and familial factors were related to risk of breast cancer (Brinton 1982). Models combining these risk factors were developed to estimate overall breast cancer risk in individuals (Gail 1989).

The Gail (1989) model includes the risk factors shown in table 2 although only a limited first degree family history is used. In our clinic the expected number of cancers compared with the number observed was 0.48 using the Gail model (Amir 2003, Evans 2014). Before 2004, we used the Claus model modified by other risk factors which gave an E/O of 1.22. After 2004 the Tyrer -Cuzick model was used which includes a larger number of risk factors, including a more extensive family history and gave an E/O of 0.81 (Tyrer 2004). Recently even greater precision has been obtained by adding more risk factors including mammographic density and breast cancer risk associated single nucleotide polymorphisms (SNPs). (Tyrer-Cuzick model v8. 2017; <http://www.ems-trials.org/riskevaluator/>).

Some models assess only family history in order to help predict the probability of a gene mutation. (Mutations are now called pathological variants [PVs]). The most widely used model to predict PVs is BOADICEA (Breast and Ovarian Analysis of Disease Incidence and Carrier Estimation Algorithm (see Table 2) (Antoniou 2004). Very recently the group in Cambridge, who developed the early BOADICEA models added hormonal/lifestyle factors and also mammographic density and SNPs to the model (Lee 2019).

**Table 2: Known risk factors and their incorporation into existing risk models. The models which depend only on family history do not predict overall risk well.**

	RR at extremes	Gail (1989)	Claus (1994)	BRCA PRO (1998)	Tyler-Cuzick V6 (2017)	BOADICEA 1 (2004)	BOADICEA V CanRisk (2019)
Prediction							
Amir et al [validation study [E/O]]		0.48	0.56	0.49	0.81		Not assessed
95% Confidence interval [30]		(0.54-0.90)	(0.59-0.99)	(0.52-0.80)	(0.85-1.41)		Not assessed
Personal information							
Age (20-70)	30	Yes	Yes	Yes	Yes	Yes	Yes
Body mass index	2	No	No	No	Yes	No	Yes
Alcohol intake (0-4 units) daily	1.24	No	No	No	No	No	Yes
Hormonal / reproductive factors							

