4. *I consent to the transfer of coded data with no personal identifiers for the purpose of the current research study looking at common genetic changes associated with breast cancer risk to any sponsor of the research*
5. *I agree that the information gathered can be stored by the custodians, University Hospital of South Manchester Foundation Trust, for possible use in future ethically approved research studies as described in the information sheet.*
6. *Would you like to receive your updated breast cancer risk information? (Please tick one box below)*

Archived information that women consented to for the use in other ethically approved studies include: demographic details, family pedigree including any history of cancer (current age or age of death of any relative, type of cancer and age at diagnosis), reproductive history (age at menarche, age at first pregnancy, duration of episodes of lactation and age at menopause if applicable), history of benign breast disease (including number of benign biopsies), artificial oestrogen exposure (duration of oral contraceptive pill usage, hormone replacement or fertility drugs) and morphometric information (BMI is also assessable from self-reported height and weight estimates from the women). In addition, the database stores an absolute lifetime risk calculated using the modified Claus or Tyrer-Cuzick models. The database also contains information regarding breast cancer incidence until at least January 2015. This will be extended during the study to December 2020. Although MD was not included in the risk estimates provided as part of FH-Risk, women did consent to their MD being accessed, calculated and fed back to them and this data will be accessed under their original consent (See appendix 1).

Members of the research team who are consultants and who were also part of the FH-Risk research team have permission (as they are part of the clinical care team) to access the above data (including DNA data) which participants consented to in order to perform the recalculation of risk.

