### **Statistical Analysis Plan**

The baseline anthropometric, familial and hormonal information from the FHRPC questionnaires will be entered into the breast cancer risk prediction models under consideration (TCv8 and CanRisk) and estimates of absolute 10 year and lifetime risk to age 80 risk obtained for each woman. The performance of the models will be compared in two ways; differences in prediction of individual risk and the change in category of risk (average, moderate and high) according to NICE guidelines. The follow-up period will be taken to be the time from initial referral and first clinic assessment with risk assessment to the most recent assessment or December 1st 2020, whichever is later

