#### **1. Objectives**

Primary

- vii) To determine change in NICE categories of risk (average, moderate and high risk) when new risk factors are added to standard breast cancer risk models.

- viii) To explore how much new risk models (including MD, SNP313 and mutation testing) change risk estimates previously communicated to women in the FH-Risk study, between their first referral and their latest visit to the FHRPC
- ix) To compare 10-year and lifetime risk estimates given by Tyrer-Cuzick (v8) and the BOADICEA model (v5) (Can-Risk)

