## 3. Analysis

The primary analysis will compare the risk categories and risk scores for the risk prediction models for women at entry to the clinic (or age 40) and at last follow-up in the clinic, and will compare the risk scores given by TCv8 and BOADICEA using different model inputs.

- i) **Change in risk categories** – NICE risk categories (average, moderate and high) will be compared by creating cross tabulations of risk categories at entry and at last follow-up – the number (and percentage) of women moving up and down risk categories will be

reported and the McNemar-Bowker test will be used to determine whether the change in risk categories is statistically significant between the two time points.

- ii) **Change in 10-year and lifetime risk scores** - change in continuous risk measures (10-year and lifetime risk estimates) will be estimated from TCv8 and BOADICEA risk prediction models. Normality and skewness of 10-year and lifetime breast cancer risk scores will be assessed. Where there is evidence of non-normality scores will be transformed. Scatterplots and correlation coefficients will be used to examine the relationship between 10-year and lifetime risk estimates at baseline and at latest follow-up.

Descriptive statistics will be used to report change in risk scores from time at entry to latest follow-up and will be compared using a paired t-test. Linear regression will be used to determine which risk factors (e.g. SNP313, MD) are associated with change in risk score.

- iii) **Comparison between risk models** - descriptive statistics will be used to report risk scores from TCv8 and the BOADICEA models and differences in risk scores compared. Models will be compared using a) classical risk factors alone, b) classical risk factors plus mammographic density, as measured by BIRADS, which can be included in both models and c) classical risk factors plus mammographic density and SNPs. Scatterplots and correlation coefficients will be used to examine the relationships between models and Bland-Altman plots used to show the agreement between the models.

Secondary analysis will focus on the comparison between differences in mammographic density measures and the relationship with risk scores using TCv8.

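### The SAP measures change between two TCv8 or BOADICEA estimates, so it does not deliver the comparison with the risk women were previously given that primary objective viii and the abstract call for

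*Combined protocol and SAP*

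**What the plan says.** Primary objective viii in the SAP (1. Objectives) reads: "To explore how much new risk models (including MD, SNP313 and mutation testing) change risk estimates previously communicated to women in the FH-Risk study", with the period running from first referral to latest clinic visit. Aim ii in section 2.1 has the same target and places the communicated estimate at first clinic attendance. Section 1.1 gives a method: "Change in risk and management will be calculated by comparing given risk at the time of clinic entry compared with re-estimated risk", with density and SNPs added. Its next sentence says that risk will be estimated retrospectively at both entry and latest follow-up.

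The SAP's opening paragraph says the baseline questionnaire data "will be entered into the breast cancer risk prediction models under consideration (TCv8 and CanRisk"). The primary endpoints are "10-year and lifetime breast cancer risk and the corresponding NICE risk categories for two risk prediction models: i) TCv8 and ii) BOADICEA v5". Under 3. Analysis, the lead sentence compares output from the risk prediction models at entry (or age 40) with last follow-up. Item ii states that "change in continuous risk measures (10-year and lifetime risk estimates) will be estimated from TCv8 and BOADICEA risk prediction models". Item i cross-tabulates NICE categories at entry and last follow-up without naming where the entry category comes from. Under 2. Methods, the analysis set is women with two appointments and matching risk scores, again with no source for the entry score.

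The earlier risk is on file. According to section 3.1, "the database stores an absolute lifetime risk calculated using the modified Claus or Tyrer-Cuzick models".

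**The concern.** The study's question, stated in sections 1.2 and 1.3, is how much the new models alter risk already given, and whether NICE guidance should change as a result. That requires the given figure as the starting value. If the starting value is instead a present-day model run on old questionnaire data, the reported reclassification leaves out the part of the change that comes from replacing the tool. The result would be the effect of ageing, updated information and new factors within one model. It would not be the share of women whose communicated category has moved. Parts 2 and 3 select women by category change since their initial estimate, so the Part 1 tables would describe a different change from the one that defines those groups.

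**Working it through.** No sample size or test statistic enters this point. The check compares what objective viii needs with what each part of the SAP supplies.

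**1. Could the SAP's entry value be the figure a woman was given?** Entry to the clinic closed in 2012 (section 3.1, eligibility criteria). TCv8 was introduced in 2017 and BOADICEA V in 2019 (section 3.1, participants). The gaps are 2017 − 2012 = 5 years and 2019 − 2012 = 7 years after the last entry. So no woman can have received either figure at entry.

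**2. Where does each SAP item take its entry value?**

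| SAP item | Source of entry value |
|---|---|
| Opening paragraph | TCv8 and CanRisk run on baseline questionnaire |
| 2. Methods, analysis set | Not named |
| Primary endpoints | TCv8 and BOADICEA v5 |
| 3. Analysis, lead sentence | The risk prediction models, at entry or age 40 |
| 3. Analysis, item i (categories) | Not named |
| 3. Analysis, item ii (continuous change) | TCv8 and BOADICEA |

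No endpoint or analysis names the given risk. The age-40 alternative is a further step away from anything communicated at a first visit.

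**3. What is lost?** For lifetime risk, let G be the risk given at entry, T the TCv8 classical-factors risk recalculated at entry, and U the updated risk fed back. Then

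U − G = (T − G) + (U − T).

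The left side is what objective viii asks for. The term U − T holds ageing, updated information and new factors (and the switch to CanRisk for women carrying a pathogenic variant). The term T − G holds the change of tool and of risk horizon. The SAP's endpoints address change of the U − T kind only.

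**4. Is T − G negligible?** The protocol says it is not. Its section on Tyrer-Cuzick version 8 states that v8 runs to age 85 where v6 ran to 73 or 80, and that women would in any case come out somewhat higher than the risk given at their first appointment. The horizon difference alone is 85 − 80 = 5 or 85 − 73 = 12 years. The SAP's opening paragraph gives a third version, lifetime risk to age 80.

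**5. Can the pilot supply a size?** The pilot (section 1.2) reports 53, 40 and 13 of 106 women moving down, not moving and moving up: 50.0%, 37.7% and 12.3%, which match the printed 50%, 38% and 12%. Its comparator is the Tyrer-Cuzick model without density or SNPs, not the risk given. It bears on U − T and says nothing about T − G.

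**The case against.** The SAP is a section of the protocol, and section 1.1 does state the comparison with given risk. Read together with it, the entry categories in item i could be the given ones. Section 3.3 also plans a database of previous and updated estimates for all FH-Risk women. This stands in part. A reader might infer that the plan excludes the given risk altogether, but the documents show only that no endpoint or analysis names it. The charitable reading stays open for categories. It is not open for the continuous change, because item ii names its two models.

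Same-model recalculation is also sound for its own purpose. It isolates the added factors, which is what objective vii needs, and section 2.2 objective i is worded as change between two visits. That is a reason to keep it, not a reason to let it answer objective viii.

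Communicated change is captured elsewhere. Initial and re-evaluated estimates are extracted for the Part 2 and 3 interviewees, and Part 4 examines the first risk given. This limits the downstream harm, but these are subsets with different objectives.

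Finally, given-versus-updated change is not a clean quantity. It mixes tool, horizon, age and new factors. This is correct, and the fix must say so.

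**Conclusion.** The SAP as written does not deliver the comparison stated in section 1.1 and required by objective viii. The point is textual and rests on one assumption: that the stored lifetime risk is the figure each woman was told, which the documents imply but do not state. Its numerical size cannot be derived, because no comparison of given risk with TCv8 is reported and the split of the 954 women by original tool is not given.

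Three stronger readings are tempting but unsupported.

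- A reader might use the calibration figures to predict which women move up or down. The protocol says "Before 2004, we used the Claus model modified by other risk factors which gave an E/O of 1.22" and gives 0.81 for Tyrer-Cuzick. That inference needs a calibrated updated model and proportional scaling to lifetime risk. No TCv8 calibration in this clinic is given, and the protocol says v8 runs higher than the risk previously given without exempting women assessed by modified Claus. Table 2 also prints an interval of 0.85 to 1.41 beside the 0.81, which excludes it.
- A reader might infer that objective viii wrongly says the estimates were communicated by the FH-Risk study. The full sentence reads naturally as women in that study, and aim ii places the estimate at first clinic attendance.
- A reader might infer that change from a given 10-year risk is impossible to measure. The documents mention only a lifetime figure; they do not say that no 10-year figure was given or recorded.

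**What to change.** 1. For objective viii, name the stored given lifetime risk and its NICE category as the entry value, after confirming against clinic records that it is the figure communicated. State the source of the entry score in 2. Methods and of the entry category in item i.
2. Cross-tabulate the given category against the updated lifetime category that is fed back: TCv8, or CanRisk for women with a pathogenic variant in a high or moderate risk gene.
3. Beside it, show the given risk against the TCv8 classical-factors risk recalculated at entry. This separates change of tool from change due to ageing and new factors.
4. Report both tables by original tool (modified Claus or Tyrer-Cuzick) as recorded for each woman. The document does not settle a single changeover date: section 1.2 gives 2004 in one place and a span of 1993–2010 in another.
5. State the risk horizon of each figure, and reconcile age 80 in the SAP with age 85 in the TCv8 section.
6. Limit this comparison to lifetime risk unless a given 10-year risk is found on file.
7. Keep the same-model TCv8 and BOADICEA recalculations for objectives vii and ix.

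The cost is SAP wording, a check of the stored field and a few extra tables; no new data need be collected if the stored value is confirmed. The downside is that the given-versus-updated result combines tool, horizon, age and new factors, and must be described that way in the report.

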### ***Calculation using BOADICEA V – Can-Risk***

Collaborative work with the Cambridge team that have now produced a user-friendly risk algorithm called CanRisk from their BOADICEA programme, means we can now provide bespoke breast cancer 10-year and remaining lifetime risks especially for those who carry pathogenic variants in moderate risk genes CHEK2 and ATM that are not provided for in Tyrer-Cuzick model (Archer et al 2020). CanRisk includes the same inputs as Tyrer-Cuzick (above) but also includes additional genes. Women will be provided the CanRisk output instead of Tyrer-Cuzick when they carry a pathogenic variant in any of the high or moderate risk genes. Comparisons will also be made to identify discrepancies in 10-year risks that would mean women were in different risk categories.

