### ***Genetic testing - Assay methods***

Blood samples were taken from all women as part of the original FH-Risk study protocol, from which DNA was extracted, or pre-existing DNA samples (also previously extracted from blood) were used. *BRCA1/2* mutation testing was carried out when clinically indicated (the prior probability of identifying a mutation must have met the threshold of *BRCA1/2* likelihood probability  $\geq 10\%$  in accordance with UK clinical guidance (NICE 2013), using the Manchester score, using DNA Sanger sequencing and multiple ligation-dependent probe amplification analysis of all exons and intron/exon boundaries and more recently next generation sequencing). Relatives of those identified with *BRCA1/2* mutations were offered cascade screening for the family-specific genetic mutation. All women were genotyped for 18 SNPs that have been shown to be associated with breast cancer risk in general European populations (FGFR2, CASP8, TOX3, MAP3K, 2q, CDKN2A, 10q22, COX11, NOTCH, 11q13, 10q21, SLC4A7, 6q25.1, 8q24, RAD51L1, LSP1, 5p12, 10q). In brief, multiplex genotyping was performed using Sequenom iPLEX Gold (Sequenom, San Diego, California, USA) and TaqMan assay (Life Technologies). Intra-plate duplicates and negative controls were included in all genotyping. Genotypes were verified by Scientific Data Systems (SDS) and MassARRAY TyperAnalyze. Since the study feedback in 2013-14 further analysis (see above) has been carried out to perform a SNP313 PRS. All samples have also been sequenced for mutations in a panel of 35 genes including 14 that confer at least a moderate risk of breast cancer (Dorling et al 2020). Results of gene mutations in a panel of 35 genes are already available for all women who took part in the FH-Risk study.

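### Mutation testing is part of a primary objective, but the listed model input sets stop at density plus SNPs, and the SAP gives no rule for variant carriers

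*Combined protocol and SAP*

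**What the plan says.** SAP section 1 (Objectives) has three primary objectives, numbered vii to ix. Objective viii asks "how much new risk models (including MD, SNP313 and mutation testing) change risk estimates previously communicated to women in the FH-Risk study". The Study Summary likewise counts high- and moderate-risk gene analysis among the bases of the recalculation.

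SAP section 2 (Methods, Primary endpoints) says that both models will be assessed with three input sets. The first has classical factors only, the second adds BI-RADS density, and the last and fullest is "iii) classical factors plus mammographic density plus SNPs". SAP section 3 (Analysis), item iii, repeats them for the comparison between models, ending at "c) classical risk factors plus mammographic density and SNPs". The regression in item ii asks "which risk factors (e.g. SNP313, MD) are associated with change in risk score".

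Two other parts of section 3.1 bear on this. Under the CanRisk calculation: "Women will be provided the CanRisk output instead of Tyrer-Cuzick when they carry a pathogenic variant". Under Genetic testing: "Results of gene mutations in a panel of 35 genes are already available for all women".

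**The concern.** A primary objective names three new sources of information: density, SNP313 and mutation testing. The list of model inputs that should answer it contains two. An analyst who follows the list will produce steps for density and for SNPs and none for gene results.

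The second difficulty is what counts as a carrier's updated risk. At the consultation a carrier receives the CanRisk figure; other women, by implication, receive the Tyrer-Cuzick v8 figure. The communicated risk is therefore a composite of two models. The SAP analyses each model separately and never defines that composite as an endpoint, even though objective viii concerns change relative to what women had been told. Without a rule, two analysts could treat carriers differently and report different reclassification tables and different limits of agreement between the models.

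**Working it through.** No design figure has to be reproduced. The check is a comparison of the relevant parts of the document.

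**1. Scope of the objective against scope of the analysis**

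| Place | Density | SNPs | Mutation results |
|---|---|---|---|
| SAP Objectives, primary viii | yes | yes | yes |
| Study Summary, basis of recalculation | yes | yes | yes |
| SAP Primary endpoints, fullest set | yes | yes | not named |
| SAP Analysis iii, fullest set | yes | yes | not named |
| SAP Analysis ii, regression examples | yes | yes | not named, but the list is open |
| SAP Analysis i and ii, change over time | no input set given | no input set given | no input set given |

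The difference between the second and third input sets gives the contribution of SNPs, and that between the first and second gives the contribution of density. No pair of listed sets differs by mutation results, so their contribution cannot be obtained from them.

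**2. What each model can take**

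Section 1.2 lists BRCA1, BRCA2, PALB2, CHEK2 and ATM for BOADICEA V. Section 3.1 says that Tyrer-Cuzick does not provide for CHEK2 and ATM. Section 1.2 also names BARD1, RAD51C, RAD51D and TP53 as genes with more than a twofold risk, and these are not in its BOADICEA V list. Whether variants are entered therefore affects the two models unequally, which matters for primary objective ix (Tyrer-Cuzick v8 against BOADICEA).

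**3. Timing**

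Under Genetic testing, BRCA1/2 testing was originally done only when clinically indicated, whereas the 35-gene panel covers everyone. The SAP does not say whether a variant enters the entry score, the latest score or both.

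**4. Number of women**

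Carrier frequency is not given. Taking 1% to 10% as an assumption:

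- 954 × 0.01 = 9.5, about 10 women
- 954 × 0.10 = 95.4, about 95 women

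The base of 954 is the recalculation cohort. SAP Methods restricts analysis to women with two risk appointments and corresponding scores, so the analysed numbers would be lower.

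**The case against.** The best defence is that the input sets belong to only part of the plan. The first primary endpoint (risk and NICE category under each model) is not tied to any set, and Analysis items i and ii, which measure change from entry to last follow-up, name none. Since the Study Summary builds the recalculation on gene analysis, those items can be read as using a score that includes gene results. The regression list is open, and the CanRisk paragraph of section 3.1 plans a check for 10-year risks that would place women in different categories under the two models. This stands in part: the density and SNP components of objective viii are covered, and an overall change that includes gene results could be reported if the SAP said that this is the score analysed. It does not say so, and the sets it does list still cannot isolate mutation testing.

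The research abstract (section 1.1) speaks only of density and SNPs. If that is the intended scope, objective viii needs editing instead; either way the two must be reconciled.

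A reader might infer that carriers will be scored as non-carriers. The documents do not support that. The SAP is silent, and leaving out a test result differs from entering a negative one: section 1.2 describes Tyrer-Cuzick as estimating carrier probability from the pedigree and lists BRCA1 and BRCA2 in the family among its factors.

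A reader might also double a 17-29% lifetime risk and conclude that most moderate-risk carriers would land in the wrong category. That does not follow. The twofold figure comes from comparing cases with controls, while the risk being doubled is already raised by family history and, under Tyrer-Cuzick, already contains a pedigree-based carrier probability, so part of the effect would be counted twice.

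Finally, recruitment to Parts 2 to 4 follows the consultation and is not changed by the SAP's input sets.

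**Conclusion.** The point holds as a gap between a primary objective and the analysis specified for it. The listed input sets give no estimate of what mutation testing contributes, and the SAP leaves open how carriers enter those sets, how they enter the comparison between models, and which output is their updated risk in the NICE cross-tabulation.

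It would be too much to say that the objective cannot be answered: the shortfall is confined to the mutation-testing component of one of three primary objectives. The switch to CanRisk affects carriers only, so nothing here shows a mismatch between the analysed and communicated risk for other women. The size is unknown; about 10 to 95 of 954 women rests wholly on an assumed carrier frequency of 1% to 10%. The amendment is worth making because the data exist and the change is small.

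**What to change.** 1. Add a fourth input set: classical factors, density, SNP313 and pathogenic variant status, as each model allows. For BOADICEA V this means BRCA1, BRCA2, PALB2, CHEK2 and ATM. Note that Tyrer-Cuzick v8 does not provide for CHEK2 and ATM, and that carriers of panel genes listed for neither model cannot be scored for them.
2. State that the first three sets are run without variant test results, and whether a variant enters the entry score, the latest score or both.
3. Report carriers and non-carriers separately, including in the comparison of the two models.
4. Define the communicated composite (CanRisk for carriers, Tyrer-Cuzick v8 otherwise) as an endpoint, and report change in NICE category and in risk score from the risk first given.
5. Align the research abstract with objective viii.

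Cost: one further model run on data already held, and a few sentences in the SAP. The drawback is that carrier numbers may be small, so their results would be imprecise and mainly descriptive.
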